6.0 STUDY PROCEDURES

6.1 Schedule of Events

The procedures and assessments to be performed during each phase of the study are outlined in the Study Schedule of Events (see Table 1).

Table 1. Study Procedures Schedule of Events for SELK2-00005

Study Procedures	Screening Phase	Treatment Phase						Day 21	Day 29 Phone Call	Day 43 Phone Call	Day 57 Final Study Visit/ Early Discontinuation Visit
		Day 1 ^a (Randomization)	Day 2 (TKA)	Day 3	Day 4	Day 5 to Day 10	Day 11				
Visit Window (days)	30 days to 1 day prior to Randomization	N/A	N/A	N/A	N/A	± 2	± 2	± 2	± 2	± 2	± 2
Informed Consent	X										
Demographics	X										
Medical History	X	X ^b									
Physical Examination	X	X ^c			X ^c		X ^c	X ^c			X
12-Lead ECG	X				X						X
Vital Signs, Body Weight	X ^d	X ^d	X ^e		X		X	X			X
Chemistry, Hematology (CBC), and Urinalysis	X	X			X		X	X			X
PT/INR and aPTT	X	X			X		X	X			X
Samples for hsCRP, D-dimer analysis	X	X			X	X ^f (Day 6 Only)	X	X			X
HIV, Hepatitis B and C	X										
TKA Surgery			X								
Venography							X				
PK/PD Blood Samples (only SelK2 or adapt. arm)		X ^g	X ^h		X	X ^f (Day 6 Only)	X	X			X
Immunogenicity (only SelK2 or adapt. arm)		X ^g					X	X			X
Pregnancy Test	X ⁱ	X ⁱ									
Record Concomitant Medications and Transfusions	X	X	X	X	X	X	X	X	X	X	X
AE Assessment		X	X	X	X	X	X	X	X	X	X
IRT Randomization		X									
SelK2 Dosing (only SelK2 or adapt. arm)		X ^j									
Enoxaparin Dosing (only enoxaparin or adapt. arm)		X ^k	X ^l	X	X	X	X				

- ^a All Day 1 assessments and activities need to be completed PRIOR to randomization.
- ^b Interim medical history only to confirm no change in patient eligibility to be done prior to patient randomization.
- ^c Abbreviated physical examination only (refer to Section 6.5.2.3).
- ^d Body weight to be recorded only at Screening and on Day 1.
- ^e Vital signs (temperature, respiration rate, blood pressure, and pulse) should be collected on Day 2 prior to TKA procedure.
- ^f If patients remain in the hospital through Study Day 6, blood samples should be collected for PK/PD and Inflammatory and Thrombosis Markers of hsCRP and D-dimer.
- ^g PK, PD and immunogenicity blood sampling to occur on Day 1 prior to SelK2 dosing.
- ^h PK and PD blood sampling to occur on Day 2 prior to TKA approximately 12-24 hours after SelK2 dosing.
- ⁱ For all females of child bearing potential, a serum pregnancy test will be conducted during Screening and, for women of child-bearing potential, a urine pregnancy test must be completed prior to randomization on Day 1. Both tests must be NEGATIVE prior to randomization on Day 1.
- ^j SelK2 dosing should ONLY occur after randomization of patient to SelK2 arm (or those randomized to adaptive arm of SelK2 and enoxaparin).
- ^k If PI/site plans to dose enoxaparin prior to TKA procedure, dosing can ONLY occur after randomization of patient to enoxaparin arm and should be dosed 12 hours prior to TKA surgery.
- ^l Enoxaparin dosing on Day 2 should be administered SC 12 hours after TKA surgery.

N/A = Not Applicable; ECG=electrocardiogram; AE=adverse event; PD=pharmacodynamics; PK=pharmacokinetics; CBC=complete blood count; UA=urinalysis; PT/INR=prothrombin time/international normalized ratio; aPTT=activated partial thromboplastin time; HIV= human immunodeficiency virus; IRT=Interactive Response Technology; TKA= Total Knee Arthroplasty (Total Knee Replacement Surgery)

6.2 Screening Phase

This screening process will be conducted to confirm the patient's eligibility to participate in this study based on a review of all inclusion and exclusion criteria. The following procedures are to be performed within 30 days prior to Day 1 of the Treatment Phase (note, medical history can be used to confirm criteria as long as data was collected/verified within the 30-day screening phase):

1. Signed the Informed Consent;
2. Demographics including age, gender, race;
3. Medical history;
4. Complete physical examination (refer to section 6.5.2.3);
5. 12-lead ECG;
6. Vital signs including sitting blood pressure, pulse rate, respiratory rate, and temperature after sitting for 3-5 minutes, and body weight;
7. Collection of clinical laboratory samples (blood and urine) to be shipped to the central lab for evaluation of hematology, blood chemistry, coagulation parameters and urinalysis (See Section 6.5.2.2 for complete listing of analyses);
8. HIV antibody testing, Hepatitis B and C testing;
9. High Sensitivity C-reactive Protein (hsCRP) and D-dimer sample collection;
10. In female patients of child bearing potential perform serum pregnancy test; and
11. Record concomitant medications and transfusions.

Patients who meet all of the inclusion criteria and none of the exclusion criteria during the Screening Phase will be eligible for the study. At the Investigator's discretion, patients that are excluded from the study may be rescreened for study inclusion at a later date that is at least two weeks following the initial study exclusion. The primary reason for patient exclusions will be recorded in a screening log for patients who are not randomized.

No study-specific procedures will be performed prior to completion of informed consent by patient.

6.3 Treatment Phase

The schedule of assessments and procedures to be performed during the Treatment Phase are outlined below by Study Day and in the “Study Schedule of Events” (see Table 1).

6.3.1 Day 1

The following procedures are to be performed on Day 1. Day 1 can also serve as the day of Check-in to the hospital facility as an inpatient and serve as the beginning of the patient’s stay at the hospital study site. (Day 1 activities could be conducted as an outpatient if assurance that patient will return to facility early on Day 2 for TKA).

IMPORTANT NOTE: All the listed assessments (1-8) are to be completed PRIOR to randomization.

1. Medical history (update any additional medical history or any changes in medical history that has occurred since the time of the Screening Visit);
2. Abbreviated physical examination (refer to section 6.5.2.3);
3. Vital signs including sitting blood pressure, pulse rate, respiratory rate, and temperature after sitting for 3-5 minutes, and body weight;
4. Collection of clinical laboratory samples (blood and urine) to be shipped to the central lab for evaluation of hematology, blood chemistry, coagulation parameters and urinalysis;
5. Collection of blood samples for hsCRP and D-dimer assessments;
6. Collection of blood samples for PK, PD, and immunogenicity assessments prior to study drug dosing;
7. In female patients of child-bearing potential, perform urine pregnancy test. The urine pregnancy test must be negative before randomization and dosing of study drug; and
8. Record any new or changes to concomitant medications and transfusions.

It is preferred that procedures are performed in following order: ECG and vital signs followed by blood draws.

If all of the inclusion criteria and none of the exclusion criteria (that are immediately evaluable) are met, patients can be enrolled in the study and the following activities can be completed on Day 1.

9. RANDOMIZATION of patient using IRT.
10. If patient is randomized to the SelK2 arm or SelK2 + enoxaparin arm, SelK2 dosing should be completed on Day 1 at least 12 hours but not more than 24 hours prior to beginning of TKA procedure. Patients MUST remain in the clinic for at least 1 hour after dosing with SelK2.
11. If patient is randomized to the enoxaparin arm or SelK2 + enoxaparin arm, site may choose to give a pre-surgery dose of enoxaparin 12 hours prior to TKA surgery.
12. Assessment of AE’s.

6.3.2 Day 2

The following need to be completed prior to the start of the TKA procedure.

1. Vital signs including sitting blood pressure, pulse rate, respiratory rate, and temperature after sitting for 3-5 minutes;
2. Assessment of AEs; and
3. For patients in the SelK2 arm or SelK2 + enoxaparin arm, collection of blood samples for PK and PD assessments prior to start of TKA surgery but between 12 to 24 hours after SelK2 dosing.

Once these activities have been completed, patient can be prepared for the TKA procedure.

4. TKA procedure to be completed.

Once TKA is completed:

5. For patients randomized to the enoxaparin arm or SelK2 + enoxaparin arm, dosing of enoxaparin to occur 12 hours after TKA.
6. Recording of concomitant medications and transfusions; and
7. Assessment of AEs.

6.3.3 Day 3

Patients will remain in hospital facility during Day 3 and undergoing the following procedures.

1. For patients randomized to the enoxaparin arm or SelK2 + enoxaparin arm, dosing of enoxaparin;
2. Recording of concomitant medications and transfusions; and
3. Assessment of AEs.

6.3.4 Day 4

Patients will undergo the following procedures on Day 4.

1. Abbreviated physical examination;
2. 12-lead ECG;
3. Vital signs including sitting blood pressure, pulse rate, respiratory, and temperature after sitting for 3-5 minutes;
4. Collection of clinical laboratory samples (blood and urine) to be shipped to the central lab for evaluation of hematology, blood chemistry, coagulation parameters and urinalysis;
5. Collection of blood samples for hsCRP and D-dimer assessments;
6. For patients randomized to the SelK2 arm or SelK2 + enoxaparin arm, collection of blood samples for PK and PD assessments;
7. For patients randomized to the enoxaparin arm or SelK2 + enoxaparin arm, enoxaparin dosing;
8. Record any new concomitant medications and transfusions; and
9. Assessment of AEs.

Patients can be released from the hospital research site following completion of all assessments on Day 4.

6.3.5 Day 5 – Day 10

Patients can remain in the hospital site throughout Day 5 – Day 10 OR may be discharged from the hospital at any point during this time frame at the discretion of the site and their standard practices. Site personnel will be charged with collecting data on concomitant medications, transfusions, and assessment of AEs for each patient throughout this period.

For Days 5-10 regardless of whether or not patient is in hospital or discharged to home, patients will undergo the following procedures.

1. For patients randomized to the enoxaparin arm or SelK2 + enoxaparin arm, enoxaparin dosing.

For patient remaining in the hospital on Study Day 6, the following assessments should be done on Day 6 ONLY:

2. Collection of blood samples for hsCRP and D-dimer sample collection; and
3. For patients randomized to the SelK2 arm or SelK2 + enoxaparin arm, collection of blood samples for PK and PD assessments.

6.3.6 Day 11

Patients will undergo the following procedures on Day 11:

1. Abbreviated physical examination;
2. Vital signs including sitting blood pressure, pulse rate, respiratory, and temperature after sitting for 3-5 minutes;
3. Collection of clinical laboratory samples (blood and urine) to be shipped to the central lab for evaluation of hematology, blood chemistry, coagulation parameters and urinalysis;
4. Collection of blood samples for hsCRP and D-dimer assessments;
5. For patients randomized to the SelK2 arm or SelK2 + enoxaparin arm, collection of blood samples for PK, PD, and immunogenicity assessments;
6. For patients randomized to the enoxaparin arm or SelK2 + enoxaparin arm, enoxaparin dosing;
7. Venography;
8. Record concomitant medications and transfusions; and
9. Assessment of AEs.

Patients can be released from the hospital or clinic following completion of all assessments on Day 11.

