- 2) 40 mg dose of enoxaparin (active comparator) administered SC 12 hours after TKA surgery followed by daily injections of 40 mg enoxaparin, SC for at least 9 additional days post-surgery and up to the day of the planned venography (with the option of giving an additional 40 mg enoxaparin, SC dose 12 hours prior to TKA surgery).

Upon activation of the adaptive arm and discontinuation of the SelK2 only arm of the study, during the Treatment Phase each patient will receive either:

- 1) A single 7.5 mg/kg dose of SelK2 administered intravenously 12 to 24 hours prior to the initiation of the TKA surgery AND 40 mg dose of enoxaparin administered SC 12 hours after TKA surgery followed by daily injections of 40 mg enoxaparin, SC for at least 9 additional days post-surgery and up to the day of the planned venography, or
- 2) 40 mg dose of enoxaparin (active comparator) administered SC 12 hours after TKA surgery followed by daily injections of 40 mg enoxaparin, SC for at least 9 additional days post-surgery and up to the day of the planned venography (with the option of giving an additional 40 mg enoxaparin, SC dose 12 hours prior to TKA surgery).

Each randomized patient will undergo TKA surgery on the Day 2 of the study. Patients must stay hospital for at least 2 nights after the TKA. A mandatory venogram will be completed on Study Day 11 (\pm 2 days). Completion of venography will conclude the Treatment Phase of the study. Patients will then enter a Follow-up Phase of the study which will consist of two clinic visits on Days 21 and 57 and follow-up telephone contacts on Days 29 and 43. The final study visit occurs on Day 57 with a complete set of laboratory and safety assessments. Prior to enrollment into the study, a Screening Phase consisting of clinical and laboratory evaluations will occur within 30 days prior to randomization to assess patient's eligibility for this study. Each patient will participate in the study for up to approximately 13 weeks, including an up to 30-day Screening Phase, 11-day Treatment Phase, and a 45-day Follow-up Phase.

Test Product, Dose Preparation, and Mode of Administration:**Study Drug (SelK2):** [REDACTED]

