3.4.2 Treatment Phase

After assessment that the patient has met all Inclusion Criteria and none of the Exclusion Criteria, on the day PRIOR to the scheduled TKA surgery, the patient will be randomized into this study. Prior to dosing of any study drug, baseline safety assessments will be taken.

For those randomized to receive SelK2, patients will receive a single dose of 7.5 mg/kg SelK2 via IV administration at least 12 hours prior to but not longer than 24 hours prior to the start of the TKA surgery. The Treatment Phase of the study consists of the period from the dosing of study drug (SelK2 or enoxaparin) or the TKA (for enoxaparin arm, if enoxaparin dosing is only done after TKA) up to the day of venography (Day 11 \pm 2) or early study termination. Note that for patients randomized to receive SelK2, study drug can be dosed either the day prior to TKA (Day 1) or on the day of TKA (Day 2) as long as the dosing occurs at least 12 hours prior to but not longer than 24 hours prior to the start of the TKA surgery.

For those randomized to receive enoxaparin, patients will receive 40 mg enoxaparin administered via SC injection 12 hours after TKA surgery followed by daily SC injections of 40 mg enoxaparin for at least 9 additional days post-surgery (with the option of giving an additional 40 mg enoxaparin SC dose 12 hours prior to TKA surgery).

For those randomized to receive SelK2 and enoxaparin, patients will receive a single dose of 7.5 mg/kg SelK2 via IV administration at least 12 hours prior to but not longer than 24 hours prior to

the start of the TKA surgery and will receive 40 mg enoxaparin administered via SC injection 12 hours after TKA surgery followed by daily SC injections of 40 mg enoxaparin for at least 9 additional days post-surgery.

For all patients, the Treatment Phase will be completed on the day the venography is completed.

Patients will remain in the hospital for AT LEAST two overnights after TKA. During the Treatment Phase, efficacy, safety and PK/PD/Immunogenicity assessments will be completed for each patient.

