3.4.4 Study Diagrams for SelK2 and Enoxaparin Arms

The following diagram depicts the Screening, Treatment, and Follow-Up Phases of the study for patients randomized to receive **SelK2**:

Screening Phase	Treatment Phase				Follow-Up Phase
Screening (Maximum 30 days prior to dosing)	Day 1 Baseline Assessments Randomization Single Dose of IV SelK2 7.5 mg/kg dosed 12 to 24 hours prior to TKA	Day 2 TKA	Days 3 -11 Assessment of Efficacy and Safety	Day 11 Venography	Follow-Up Assessments Through Day 57

The following diagram depicts the Screening, Treatment, and Follow-Up Phases of the study for patients randomized to receive **Enoxaparin**:

Screening Phase	Treatment Phase				Follow-Up Phase
Screening (Maximum 30 days prior to dosing)	Day 1 Baseline Assessments Randomization Optional Enoxaparin 40 mg SC at least 12 hours pre-TKA	Day 2 TKA Enoxaparin 40 mg SC 12 hours post-TKA	Days 3-11 Assessments of Efficacy and Safety Enoxaparin 40 mg SC, QD	Day 11 Venography	Follow-Up Assessments Through Day 57

IF Adaptive arm is activated:

The following diagram depicts the Screening, Treatment, and Follow-Up Safety Phases of the study for Patients Randomized to Receive **SelK2 and Enoxaparin**:

Screening Phase	Treatment Phase				Follow-Up Phase
Screening (Maximum 30 days prior to dosing)	Day 1 Baseline Assessments Randomization Single Dose of IV SelK2 7.5 mg/kg dosed 12 to 24 hours prior to TKA Optional Enoxaparin 40 mg SC at least 12 hours pre-TKA	Day 2 TKA Enoxaparin 40 mg SC 12 hours post-TKA	Days 3-11 Assessments of Efficacy and Safety Enoxaparin 40 mg SC, QD	Day 11 Venography	Follow-Up Assessments Through Day 57

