5.2.2 Dosing of Enoxaparin

For those randomized to receive enoxaparin, patients will receive 40 mg enoxaparin administered via SC injection 12 hours after TKA surgery followed by daily SC injections of 40 mg enoxaparin through and including Day 11 (\pm 2 days). Daily dosing of enoxaparin should continue until the venogram is completed. At the discretion of the PI, sites also have the option of giving an additional 40 mg enoxaparin SC dose 12 hours PRIOR to TKA surgery.

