5.2.3 Adaptive Arm: Dosing of SelK2 and Enoxaparin

When the adaptive arm is activated, for those randomized to receive SelK2 and enoxaparin in combination, patients will receive a single dose of 7.5 mg/kg SelK2 via IV administration at least 12 hours prior to but not longer than 24 hours prior to the start of the TKA surgery. SelK2 will be given as an approximately 100 mL IV infusion over approximately 30 minutes (\pm 15 minutes). Additionally, patients will receive 40 mg enoxaparin administered via SC injection 12 hours after TKA surgery followed by daily SC injections of 40 mg enoxaparin through and including Day 11 (\pm 2 days).

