Synopsis Safety Section And Section 3.5 Safety and efficacy Assessments And Section 6.0 Study Procedures	Add “of child bearing potential” to description of women for which serum pregnancy test should be completed
Section 5.2.3. Adaptive Arm: Dosing of SelK2 and Enoxaparin	Section 5.2.3 Delete: At the discretion of the PI, sites also have the option of giving an additional 40 mg enoxaparin SC dose 12 hours PRIOR to TKA surgery. If both SelK2 and enoxaparin dosing are planned for prior to the start of the TKA surgery, SelK2 should be given prior to the enoxaparin dosing.
Synopsis, Statistical Methods and Section 10.3.3 Efficacy Analysis	Clarify that all primary and secondary analyses will compare SelK2 only, SelK2 and Enoxaparin, and Enoxaparin only arms

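### Current sections conflict on whether patients in the SelK2 + enoxaparin arm may receive enoxaparin before surgery, and Table 1 does not resolve it

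*Combined protocol and SAP*

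**What the plan says.** Two current places allow the dose in the combination arm.

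- Section 6.3.1 (Day 1), item 11: for patients "randomized to the enoxaparin arm or SelK2 + enoxaparin arm, site may choose to give a pre-surgery dose of enoxaparin", timed 12 hours before TKA.
- Section 3.4.4, combination-arm diagram, Day 1 cell: "7.5 mg/kg dosed 12 to 24 hours prior to TKA Optional Enoxaparin 40 mg SC at least 12 hours pre-TKA".

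Three current places start that arm's enoxaparin after surgery and do not mention an earlier dose.

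- Section 5.2.3: "Additionally, patients will receive 40 mg enoxaparin administered via SC injection 12 hours after TKA surgery".
- Section 3.4.2, combination paragraph: "the start of the TKA surgery and will receive 40 mg enoxaparin administered via SC injection 12 hours after TKA surgery".
- Synopsis, Duration of Treatment, adaptive-arm list: "TKA surgery AND 40 mg dose of enoxaparin administered SC 12 hours after TKA surgery".

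For the enoxaparin-only arm the option is written out. Section 5.2.2 says that "sites also have the option of giving an additional 40 mg enoxaparin SC dose 12 hours PRIOR to TKA surgery", and 3.4.2 and the synopsis carry it in parentheses.

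Table 1 points both ways. The enoxaparin row is labelled as covering the enoxaparin and adaptive arms and has a Day 1 entry. Footnote k, attached to that entry, says "dosing can ONLY occur after randomization of patient to enoxaparin arm and should be dosed 12 hours prior to TKA surgery" and does not name the adaptive arm.

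**The concern.** Section 6.3.1 is the procedure list that a site works from on Day 1, and 5.2.3 is the section that defines the combination regimen. A site relying on one could give enoxaparin on top of SelK2 before surgery. A site relying on the other would not.

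The primary safety outcome is the composite of major and clinically relevant non-major bleeding over the Treatment Phase. Under 3.4.2 that phase runs from study drug dosing, so bleeding after a pre-operative dose counts. Sections 1.4 and 10.5 make activation of the arm depend on a judgement that the combination adds no safety risk. That judgement needs one defined regimen. If the rule varies by site, the combination arm is a mixture of two regimens, and its bleeding and VTE rates describe neither one cleanly.

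**Working it through.** The check is a comparison of text. No sample size, power or event-rate figure enters it.

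**1. Combination-arm instructions side by side**

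| Place | Pre-operative enoxaparin, combination arm | Pre-operative enoxaparin, comparator |
|---|---|---|
| 6.3.1 item 11 | allowed | allowed |
| 3.4.4 diagrams | allowed | allowed |
| 5.2.3 (combination) and 5.2.2 (comparator) | not mentioned | allowed |
| 3.4.2 | not mentioned | allowed |
| Synopsis, Duration of Treatment | not mentioned | allowed |
| Table 1 row label, Day 1 entry | included | included |
| Table 1 footnote k | not named | named |

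Two places permit the dose and three give post-operative enoxaparin only. Table 1 falls on both sides. Footnote j, directly above footnote k, does name the adaptive arm for SelK2 dosing, so the silence in k is noticeable. The row label still prevents the table from counting as clear evidence for either reading.

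**2. Which way the sponsor meant it**

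The conflict stands on current text alone. The Listing of Significant Protocol Modifications is used only as evidence of intent. It records "Section 5.2.3 Delete: At the discretion of the PI, sites also have the option of giving an additional 40 mg enoxaparin SC dose", and it shows the combination text in 3.4.2 and the synopsis being added without the option. Item 11 of 6.3.1 and the 3.4.4 diagram therefore look like conforming edits that were missed.

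**3. Order of the two drugs**

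- Under 6.3.1, SelK2 is given 12 to 24 hours before TKA (item 10) and enoxaparin 12 hours before (item 11). SelK2 cannot then fall after enoxaparin; at the limit the two coincide.
- Under the 3.4.4 diagram, enoxaparin is given 12 hours or more before TKA. Enoxaparin at 24 hours and SelK2 at 12 hours would satisfy it. Only the diagram leaves the order open.

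**4. What a mixed rule does to the comparison**

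Randomization stays stratified by site after activation (5.1.3), so a site's practice is spread over both arms. The contrast within a site still depends on the rule followed:

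- pre-operative dose given in both arms: SelK2 against no SelK2 on the same enoxaparin schedule;
- pre-operative dose given to controls only: SelK2 with one fewer enoxaparin dose against enoxaparin with the extra dose;
- option not used: same enoxaparin schedule in both arms.

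**5. Patients concerned**

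Sections 3.2 and 4.0 plan about 95 combination patients. At 2:1 allocation (5.1.3), concurrent controls number 95 / 2 = 47.5, so about 47 or 48. They keep the option under either reading.

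**The case against.** The strongest reply is that omission is not prohibition. None of 5.2.3, 3.4.2 or the synopsis forbids the dose, and silence is not always meaningful here: the post-activation list in Section 3.1 also leaves the option out for controls, who have it elsewhere. On that view 6.3.1 merely adds detail. A reader might infer that 5.2.3 bans the dose; it does not. What remains is that 3.4.2 and the synopsis set the two regimens out together and give the option to one only, and the modifications listing records its removal from 5.2.3. A site cannot tell from current text which instruction governs.

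A reader might also take three stronger points from this.

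- *Table 1 supports the post-operative reading.* It does not do so cleanly, because the row carrying footnote k covers the adaptive arm.
- *6.3.1 allows enoxaparin before SelK2.* Its own timings exclude that. A sequencing rule that appears only as deleted text in the modifications listing is not an error in the current plan.
- *Per-Protocol results are at risk.* Section 10.2 excludes only major violations that affect efficacy, Section 10.3.3 makes that analysis supportive to mITT, and nothing suggests that a dose 6.3.1 permits would be classed as a major violation.

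Finally, restoring the option everywhere would keep the enoxaparin rules equal in both arms, which is cleaner for isolating SelK2. That argument is fair, but it runs against the recorded deletion from 5.2.3.

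**Conclusion.** The inconsistency is real and lies in current operative text. It matters only if the adaptive arm is activated, concerns one discretionary 40 mg dose, and applies to about 95 planned combination patients. The SelK2-only comparison is not affected.

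The consequence is a combination regimen that may differ between sites in whether both antithrombotic drugs are given before surgery, with a bearing on the primary bleeding outcome. The documents do not say how many sites would use the option or which section they would follow, so no effect on bleeding or VTE rates can be calculated. A reader might infer that the combination comparison is biased; the documents support only that its regimen is not uniquely defined. The direction of the correction rests on reading the deletion from 5.2.3 as the sponsor's intent for the whole arm.

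**What to change.** Before the adaptive arm opens, make the text agree with 5.2.3:

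1. Remove the combination arm from 6.3.1 item 11.
2. Remove the optional pre-operative enoxaparin dose from the combination-arm diagram in 3.4.4. This also closes the only place where the order of the two drugs is open.
3. State in Table 1 footnote k that the Day 1 enoxaparin dose does not apply to the adaptive arm, which settles the row label.
4. Tabulate pre-operative enoxaparin use by arm.

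The cost is three wording edits and one table from dosing records, with no added patients or procedures. Because dosing is affected, Section 12.5 requires a protocol amendment with joint approval by the sponsor and the investigator, and Section 12.6 requires the ethics committee or review board to be informed.

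There is a scientific price. Controls keep an optional pre-operative dose that combination patients do not have. That difference belongs to the randomized regimens, but it limits attribution of a bleeding or VTE difference to SelK2. The tabulation in step 4 shows how often it arises. If the sponsor prefers equal enoxaparin rules in both arms, the alternative is to restore the option in 5.2.3, 3.4.2, the synopsis and footnote k, together with an explicit order for the two drugs. Either way, one instruction should apply throughout.
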